3.0 Methods

3.1 Study Design: Single arm pilot and feasibility study.

Outcomes;

Primary: Participant Satisfaction	Items on f/u survey and qualitative interview			
Secondary:				
Feasibility	Successful recruitment, Successful sensor wears time			
	20/22 days, Data retrieved from sensor successfully			
Weight Change	Weight at final visit – weight at 2 nd visit			
Knowledge of Low Carbohydrate Eating	Low Carb Knowledge Scale – final - baseline			
Cravings and Hunger	Ratings on food logs			
Intention to continue Low Carbohydrate eating	final survey question			
Side effects of CGM wear, Low Carbohydrate eating	Side effect log			
Utility of CGM feedback for changing diet	Qualitative Interview			

3.2 Study Population and Recruitment:

As identified though MiChart and Data Direct searches, 10-15 adult Michigan Medicine patients who qualify based on inclusion and exclusion criteria will be contacted via US Mail regarding their participation in our study. This letter will explain the study and its requirements and will be accompanied by an opt-out postcard that can be returned if the patient no longer wishes to be contacted. Those who do not return the postcard will be contacted via telephone with further information about the study. Recruiting will also be accomplished through a posting on the UM Health Research website as well as printed materials such as fliers and brochures. Interested and eligible participants will be scheduled to attend a one-on-one in-person baseline visit with the study coordinator at Livonia Health Center.

3.3 Inclusion/Exclusion Criteria:

- 21+ years of age
- A1C 5.7 to 6.4
- No Diabetes medication including Metformin
- BMI >30
- Must speak, read, and write in English
- Must have a phone
- Must have a computer
- Interested in changing diet to improve health
- No current pregnancy
- No previous Bariatric surgery
- Must not classify as either Vegan or Vegetarian
- Must be a patient at the Livonia Health Center

3.4 Informed Consent: At the baseline assessment the Research Coordinator will thoroughly review the Informed Consent document with the participant. If valid informed consent is freely given the baseline data collection will begin.

3.5 Phase One, In-Person Appointment:

- Obtain a valid informed consent
- Baseline measurements including weight, height, and blood pressure

- Power point presentation outlining the study and the participant's role in Phase One.

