- Teaching on continuous glucose monitor and how it will be used to monitor their blood glucose reactions to the food that they consume.
- Application of an Abbott Libre Pro sensor (no real time feedback) to the backside of the participant's nondominant arm.
- The participant will be asked to:
 - o leave the sensor in place for a period of 11 days
 - o complete a food log during that time, documenting what they consume
 - o Rate their postprandial hunger and fatigue 2 hours after eating
- Participants will be given a wrapped copy of the book, "Always Hungry" by [name] and asked not to open the book until after they receive their health check phone call on Day 5.
- Participants will then be given the Study Coordinators contact information
- Appointments for the second and third meeting will be made.

3.6 Health Check Phone Call: Approximately 5 days after each new sensor is p

- A member of the study team will call the participant to ensure that the participant is experiencing no ill effects from wearing the sensor.
- The study team member will also answer any questions that the participant may have regarding the sensor or the study in general.
- The study team member will then ask the participant to open their copy of the book, "Always Hungry" by David Ludwig and encourage the participant to read chapters 1-5.

3.7 Phase Two, Intervention Appointment: Approximately 11 days after their first appointment:

- Participants will return to the Livonia Health Center for a second one-on-one meeting.
- Weight, and blood pressure will be repeated.
- Participants will then take a brief survey.
- The Abbott Libre Pro sensor will be removed.
- Data captured by the sensor will be uploaded and printed for the participant.
- All uploaded data will be reviewed with the participant and compared to their completed food Log.
- Participants will be shown a Power Point presentation that discusses their role in Phase Two.
- Abbott Libre **personal** sensor (with meter for real time feedback) will be applied to the back of the participants non-dominate arm.
- Participants will be taught about carbohydrates and the benefits of eating a low carbohydrate diet.
- Participants will be given a new food log and asked to:
 - o document the food that they consume
 - o rate their postprandial hunger and fatigue two hours after eating
 - o document their blood sugar before and two hours after eating

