- Participants will be given multiple resources to assist them in determining how many carbohydrates are in the foods they consume.
- Participants will be given the book entitled, "The Calorie King, Calories, Fat, and Carbohydrates," which lists the calorie, fat, and carbohydrate content of various foods.
- Possible side effects of low carbohydrate diet will be discussed with the participant and information on how to mitigate the effects of the diet will also be provided.

- Patients will be instructed to fill out a side effect log as well as their diet log during this phase.
- Participants will complete an information sheet, voluntarily suppling their address as well as any information about food allergies they may have.
- Participants will choose two recipes from a group of five options that they would like to make for themselves and/or their immediate family.
- **3.8 Grocery Delivery:** Approximately two days following the participants second visit all of the ingredients for one of their chosen recipes will be delivered to the address provided. All of the ingredients for the second recipe that the participant has chosen will be delivered approximately five days later.
- **3.9 Follow-Up Visit:** Approximately 11 days after the intervention visit:
 - Participants will have the second sensor removed.
 - Data obtained by the sensor will be uploaded and printed out for their review.
 - Participant's data will be compared to their completed food log.
 - Participants will also be provided with a letter to take to their Primary Care Physician (PCP) explaining the study and asking for a prescription for an Abbott Libre personal sensor so that the participant may continue tracking their blood glucose levels following the study.
 - Participants will take the "Completion Survey"
 - Participants will receive either a check or a voucher for \$25.00 for completing the survey and all three of their in-person appointments.
 - Participant wishes to continue wearing a CGM and has found that it has been an effective way to assist them
 in consuming a low carbohydrate diet, they will be given a letter addressed to their Primary Care Physician
 asking for a prescription to continue using the Abbott Libre personal CGM sensors and reader.

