- **3.10 Semi-structured qualitative interview:** After the participant has completed all three visits with the Research Coordinator and have worn both CGM sensors, they will receive a telephone call from the studies mixed methods interviewer who will conduct a semi-structured qualitative interview. Each participant will be asked a series of questions concentrating on their satisfaction with the CGM sensors and devices, how their diet has been effected by wearing the CGM sensors, and how they feel about having been diagnosed with pre-diabetes.
- **3.11 6-month Follow-up Telephone Interview:** A member of the research team will call each participant six months after they have completed all three appointments to conduct a second semi-structured qualitative interview. Each participant will be asked a series of questions designed to ascertain whether or not the study has had continued impact on their diet and ability to prevent the transition to Type 2 Diabetes. The participant will be asked questions like whether or not they have continued their effort to avoid carbohydrates and whether or not they have worked with their Primary Care Physician to obtain their own personal continuous glucose monitor.

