6.1 Timeline

	1	2	3	4	5	6	7-12?
Start – June 1	X						
Recruitment	X	X					
Data Collection	X	X	X	X		X	
Analysis				Х	Х	Х	
Manuscript							V
Preparation							X

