3.10 Semi-Structured Qualitative Interview

- After all three in-person visits have been completed
- The Mixed Methods Interviewer will call the participant to discuss the study
- Questions will revolve around the participant's satisfaction with the CGM sensors and the phase-two reader, how their diet was effected by the CGM sensor and information that it gave them, and how they feel about having been diagnosed with pre-diabetes.

3.11 6-Month Follow-up Telephone Interview

- Six months after the participant has completed all three study visits they will receive a telephone call from the studies Mixed Methods Qualitative Interviewer.
- The Interviewer will ask questions about the impact that the study has had on their diet, whether or not they have become diabetic and whether or not they made any effort to obtain their own continuous glucose monitor.

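### Does the section 6.1 timeline leave no room for the six-month telephone interview?

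*Protocol*

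**What the plan says.** The protocol states the timing of the second interview twice. Section 3.11 in the main text says: "A member of the research team will call each participant six months after they have completed all three appointments". The detailed procedures at the end of the document repeat it: "Six months after the participant has completed all three study visits they will receive a telephone call". Both count from completion of the third visit, not from enrolment or study start.

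The visits are close together. The second is set at "Approximately 11 days after their first appointment" (section 3.7) and the third at "Approximately 11 days after the intervention visit" (section 3.9).

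Section 6.1 is a one-table project timeline with a June 1 start. Its rows are marked as follows:

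- Recruitment: columns 1-2.
- Data collection: columns 1-4 and column 6, with column 5 blank.
- Analysis: columns 4-6.
- Manuscript preparation: the last column only, headed 7-12 with a question mark.

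No unit is given for the columns. The outcomes table in section 3.1 opens with "Primary: Participant Satisfaction", measured by follow-up survey items and the qualitative interview. Its secondary list does not include the six-month call.

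**The concern.** Read as months, the grid ends data collection and analysis at month 6. A call counted six months from a third visit cannot happen that early in a study that starts in month 1. The lone data-collection mark in column 6, after a blank column 5, suggests that someone may have placed the six-month interview by counting from study start, although the document does not say so.

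Two things could go wrong. Staff working from the grid might call early and still label the result six-month, or the interviews might arrive after the scheduled analysis has closed. This call is the only planned contact after the first interview. It is also the only planned source on lasting diet change, progression to diabetes and efforts to obtain a personal monitor, so a mistimed or unanalysed set of calls would be a real loss for those questions.

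**Working it through.** **Inputs.** Visit 1 to visit 2 is about 11 days (section 3.7). Visit 2 to visit 3 is about 11 days (section 3.9). The call comes 6 months after visit 3 (section 3.11, both places). The start is June 1, recruitment is in columns 1-2, and the last data-collection and analysis marks are in column 6 (section 6.1). Assumption: columns are calendar months, with column 1 = June, so month 6 ends on November 30.

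**Formula.** Visit 3 = visit 1 + 11 + 11 = visit 1 + 22 days. Call due = visit 3 + 6 calendar months.

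| Case | Visit 1 | Visit 3 | Call due | Month | Days after Nov 30 |
|---|---|---|---|---|---|
| First day of study | June 1 | June 23 | December 23 | 7 | 23 |
| Last day of recruitment | July 31 | August 22 | February 22 | 9 | 31 + 31 + 22 = 84 |
| Visit 3 on the last day of column 4 | not applicable | September 30 | March 30 | 10 | 31 + 31 + 28 + 30 = 120 |

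**Can the grid be met?** Working backwards, a call due by November 30 needs visit 3 by May 30 and visit 1 by May 8. That is 24 days before the June 1 start. Even counting six months from visit 1 on the first day gives December 1, still month 7. The looseness in the 11-day intervals therefore cannot close the gap, and 0 of 10-15 calls fit.

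**How firm is each end?** Month 7 is firm under the month reading. Month 9 follows from recruitment in columns 1-2. Month 10 requires third visits in column 4, but recruitment ending on July 31 puts the last third visit at about August 22. The column 4 mark could simply cover the first qualitative interview (section 3.10). Months 7 to 9 is the supported range.

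**If staff followed the grid instead.** Calls squeezed in on November 30 would come 7 + 31 + 31 + 30 + 31 + 30 = 160 days after a June 23 third visit, and 9 + 30 + 31 + 30 = 100 days after an August 22 third visit. The rule asks for 160 + 23 = 183 and 100 + 84 = 184 days. The label would then be wrong by 23 to 84 days.

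**What depends on the call?** Set against section 3.1, satisfaction comes from the follow-up survey and qualitative interview, and the first interview (section 3.10) supplies the latter soon after visit 3. Feasibility, weight change, knowledge, cravings, intention and side effects come from the visits, surveys and logs. All of this is in hand by about the end of August plus the first interview, so analysis in columns 4-6 is workable as drawn.

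**The case for a change.** The case for a change is that two parts of the current text cannot both be followed. The protocol states its own schedule and contradicts it, so this is not a detail left for the analysis plan. Months are the natural unit, given a calendar start date and columns running to 12. The marks line up with the column headings in the table as read. The question mark on the last column makes its length uncertain but does not put data collection into it. Correcting the table would cost almost nothing and would need no extra participants, visits or procedures.

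Most of that stands: on the month reading, the mismatch is a fact. Three things weaken its force. First, the unit is not stated, and the table came through extraction with visible damage (the manuscript row is split and carries a stray character), so a lost or shifted mark cannot be excluded. Second, the grid is a provisional project chart, and the authors themselves marked the period after column 6 as open. Third, the harm needs staff to set aside an explicit instruction, given in the procedures that tell the interviewer when to call, in favour of that chart. A low cost of correction does not by itself show a benefit.

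**Conclusion.** The discrepancy is a clerical slip in a planning table and does not call for a change to the plan. Assuming the columns are months from June 1, the six-month calls fall due in about months 7 to 9, 23 to 84 days beyond the last marked month, and none of the 10-15 falls within it. The operative rule is unambiguous and stated consistently in both places. Staff who follow it will call inside the open 7-12 period, while the manuscript is being prepared, and the interviews can be read and reported then.

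The primary and secondary outcomes in section 3.1 do not use this call, and their analysis is feasible as scheduled. No sample size, estimate or conclusion would differ if the grid were redrawn. The judgement rests on staff working from section 3.11 rather than from the chart, which is the sensible expectation when one is a written procedure and the other carries a question mark.

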4.0 Feasibility

This is a pilot and feasibility study. Our team has extensive experience using older style CGMs in type 1 diabetic patients and we have conducted preliminary usability testing in 10 study staff using the new CGM sensors, however we have not conducted this type of intervention in patients with pre-diabetes recruited in a clinical

setting. Additionally, we have experience successfully teaching a cohort of patients with pre-diabetes to eat a lower carbohydrate diet for weight loss. We will incorporate some of the lessons learned from that pilot into this pilot and feasibility study as well. Recruitment for 10 to 15 individuals with pre-diabetes from the Livonia Health Center should not be difficult and the Livonia medical director has already agreed to support the trial. A full time research coordinator who is also an experienced medical assistant and who has experience using CGM will be conducting study procedures at Livonia

6.1 Timeline

	1	2	3	4	5	6	7-12?
Start – June 1	X						
Recruitment	X	X					
Data Collection	X	X	X	X		X	
Analysis				Х	Х	Х	
Manuscript							V
Preparation							X

3.2 Study Population and Recruitment

- Data Direct will be used to identify those patients at the Livonia Health Center that have pre-diabetes.
- Once those patients have been identified a MiChart search will be used to determine if other eligibility criteria are met and to obtain potential participants addresses.
- A letter explaining the study and the basic requirements for participation will be sent to the primary address of the potential participants.
- The letter will be sent along with a post card asking that the participant return the card if they do not wish to be contacted further.
- If we do not receive the post card back in the mail it will be assumed that the potential participant would like to participate in the study.
- A follow up phone call will be made to all of those identified and did not return the post card to explain the study in further detail and to make arrangements for their first appointment.
- In addition to the Data Direct search, a post about the study will be placed on the UM Health Research website asking for potential volunteers that meet the outlined criteria.

3.4 Informed Consent

- Each page of the informed consent document will be reviewed with the potential participant.
- After it is determined that the participant understands the Informed Consent document; the participant will sign and initial in appropriate places and freely give their consent to be part of the study.

3.5 Phase One, First In-Person Appointment

• Upon completion of this appointment the participant will receive either a check or a voucher for \$25.00 in gratitude for taking the survey and for taking part in this study.

3.5.1 Measurements

Weight:

- Participants will be asked to remove their shoes, coats, and any other heavy outerwear.
- Participants will be asked to set down any other belongings and empty their pockets of anything that may add additional weight to the scale.
- Participants will then stand on the Livonia Health Center Clinic scale to be weighed.
- Weight will be recorded on the Patient's measurement record labeled with their study
 ID only

Height:

Participants will leave their shoes off and will stand with their back against the standard
 U of M clinic wall mounted height measurement board.

- Participant will push their heels back as far as they are able and will stand fully erect with shoulders back against the height board.
- The height indicator will be set to rest on the top of the participant's head
- The height will be documented on the Patient's measurement record labeled with their study ID only.

Blood Pressure:

- Participant will be asked to sit in a chair with their feet flat on the floor.
- The appropriate sized arm cuff will then be applied to either the patient's upper right or upper left arm
- The patient will leave their arm outstretched at an angle of approximately 90 degrees to their torso and resting on either the DynaMap Automatic Blood Pressure machine stand or something of similar height.
- Patient's blood pressure will then be obtained via the automatic DynaMap blood pressure machine standard to all U of M clinics.
- Blood Pressure will be documented on the patient's measurement record and labeled with their study ID only

o HbA1c:

 The participant's most recent A1c level will be obtained from Michart and documented along with the date it was resulted on the patient's measurement record and labeled with their study ID only.

3.5.2 Baseline Survey

- Participants will be asked to complete a brief, survey of approximately 45 questions over a period of approximately 15 minutes.
- Survey will contain questions relating to: diabetes and diet experiences, hunger and cravings, post-prandial fatigue, carbohydrate knowledge, current attitudes about health, and numeracy.

3.5.3 PowerPoint Presentation

- Participant will be shown a series of slides describing the scope of the study as well as how the study will progress and what the participant's requirements are.
- The Participant will be given a printed copy of the slides to review
- The Study Coordinator will review each slide along with the participant, stopping to answer any questions that may arise.

3.5.4 Abbott Freestyle Libré Pro and Sensor

- Participant will wear an Abbott Libre Pro sensor on their arm for a total for 11 days
- The first day the sensor will be adjusting to the participants' unique physiology so that the most accurate blood glucose levels and estimated A1c will be reported.
- The participant will receive no real time feedback.

3.5.5 Continuous Glucose Monitor Application

- The application of the device will be explained in detail to the participant prior to application.
- The Participant will expose the upper portion on the backside of their non-dominate arm
- The medically trained Study Coordinator will use an alcohol wipe to clean a large circular area around where the CGM sensor is to be applied.
- After the alcohol dries the Study Coordinator will use a Skin-Tac wipe to create an adhesive surface in an area around where the CGM sensor is to be applied.
- The CGM sensor will be removed from the packaging and assembled according to packaging instructions and training.
- The Sensor application device will then be place gently against the application site and the plunger will be pushed in with slight force and will remain pushed in for 2 seconds.
- The sensor applicator will then be removed leaving the sensor in place.
- The applicator will then be discarded.

3.5.6 "Always Hungry?" by [name]

- Participants will receive a wrapped copy of this New York Times #1 Bestselling book.
- Participants will be asked not to begin reading the book until Day 5 of Phase 1, after they receive their Health Check phone call.
- This book, broken in to 3 phases describes the science behind why our bodies gain weight, store fat, and how the food that we eat impacts our ability to change that.
- Contains multiple low-carbohydrate, high fat recipes and meal plans to assist in changing diet and increase knowledge about the foods that your body needs.

3.5.7 Phase One Food Log

- Participants will be asked to complete a daily food log
- Log asks participants to write down the food that they eat and what time they are it.
- Participants are asked to record their food intake in general terms rather than breaking it down
 in to chloric content, Protein content, or carbohydrate content
- Approximately 2 hours after eating participants will also document their level of hunger and post-prandial fatigue

3.5.8 Follow-Up Appointments

- Participants will be directed to the Reception Desk at the Livonia Health Center so that a member of the front desk staff can assist them in making their follow up appointments.
- These appointments will then be written down on a blank Calendar provided to each participant so that we can ensure that they are aware of when to arrive to remove their first

sensor, when to expect their Health Check phone call, and when visits two and three will take place.

